5.3 Subject withdrawal

- 1) A patient's attending physician can withdraw the patient at any time if (s)he decides that continuation in the study poses a risk for the patient.
- 2) If a parent rescinds permission a patient's participation in aerosol therapy ceases.
- 3) If there is an adverse event requiring discontinuation of the aerosolization administration the patient will be withdrawn from further study interventions.

Patients withdrawn by physicians or because of an adverse event will continue to have all data extracted from the medical records and included in safety evaluations.

Patients withdrawn by parent request will have all data collected from the medical record both before and after withdrawal from active participation in the trial. The provision for continued data collection is explicit in the informed consent and that data is necessary to have inclusive data on safety.

6. TREATMENT OF SUBJECTS

6.1 Aerosolization of Infasurf

The aerosol is generated using a Solarys® Aerosol Delivery system adapted for premature newborns. The distal tip of a catheter is fixed to a proprietary adapter for premature and term infants with RDS. The adapter has a shape similar to a neonatal pacifier. The nipple tip is actually an inverted dome that prevents the cannula tip from being obstructed by oral or pharyngeal tissues and protects delicate tissues from abrasion by the tip of the cannula. The distal tip exits just a few millimeters from the end of inverted tip of the "nipple" and delivers the aerosol into oropharynx. A fine aerosol mist is produced at the end of the catheter. A schematic of the set-up is in Appendix C.

Newborns are obligate nose breathers. Typically, non-intubated RDS patients have a \geq 3 liter/kg/minute flow of gas passing by the nose under a positive pressure. The baby inhales from, and exhales into, that flow. Newborn babies with RDS have tachypnea, \sim 60 breaths/minute, and have low tidal volumes, \sim 5 mL/kg/ breath. Less than 10% of the nasally delivered respiratory support is inhaled. The aerosol is generated in the oropharynx so when the baby inhales aerosol is drawn into the lung. When the baby exhales, some of the aerosol is exhaled, but some remains in the lungs and supplements the surfactant already there.

The Solarys aerosol works by slowly propelling the Infasurf suspension down a small central tube in the Solarys system at a rate of approximately 0.19 ml/minute. Simultaneously an air-oxygen mixture (set by the baby's respiratory needs) is propelled down 5 tiny tubules surrounding the liquid filled tube at a rate of ~0.9 liter/minute. As the liquid exits the distal end of the central tube the gas exiting from the surrounding tubules generates the aerosol mist.

Dose: A dose equal to twice the current instilled dose 210 mg/kg body weight (6 ml/kg body weight) will be aerosolized. That will require approximately 32 minutes/kg body weight. Lung deposition of aerosol is small, usually less than 25% of the dose so even an aerosol of 6 ml/kg body weight will result in a much lower lung delivered dose than the current practice of instillation of 105 mg/kg/dose.

Re-dosing: Up to 2 re-dosings are allowed once 4 hours has passed since the start of the last dose. The indication for re-dosing will be:

- 1) a positive response to the previous dose, defined as improvement in respiratory function, and
- 2) a subsequent deterioration in respiratory function, and
- 3) no adverse event during the initial dose.

Usual Care: There will be no protocol driven interventions in the usual care group. Use of pacifiers as tolerated in these patients is encouraged to decrease the incidence of loss of continuous airway pressure through the mouth.

Sham therapy has not been included because it cannot produce an effective masking of treatment assignment to care givers because of both the presence of residual Infasurf in the mouth and stomach and there is a reliable decrease in inspired oxygen requirement by the end of aerosolized Infasurf therapy.

Separation of the effect of additional gas infusion derived from aerosolized Infasurf effect by sham treatment is unnecessary. Pressure in the airway is set by the nasal therapy and that therapy will be adjusted, if necessary, to maintain the airway pressure ordered by the supervising provider. The tidal volume of spontaneous breathing participants is affected only by the airway pressure not by the volume of bias flow. Usual care patients will have the positive airway pressure set and adjusted as their respiratory status requires by their supervising provider.

The decision not include a sham procedure was also based on the concern of interrupting and/or modifying ongoing respiratory support in fragile newborns with RDS to implement the sham. Such an intervention has no reasonable expectation of benefit for the subject but does have some potential for adverse consequences. There will be no protocol driven interventions in the usual care group.

6.2 Other treatments

Participation in this trial will not restrict participating patients from any other medication or therapeutic intervention deemed appropriate by their care givers.

6.3 Subject Compliance No compliance concerns for NICU patients

7. ASSESSMENT OF EFFICACY OF AEROSOLIZED INFASURF

7.1 Parameters

- 1) Comparison of requirement for instilled surfactant to "usual care" over 72 hours.
- 2) Comparison of severity of RDS to "usual care" over 72 hours.
- 3) Comparison of duration of respiratory support for RDS to "usual care" up to 7 days.
- 4) Comparison of incidence of pulmonary complications of RDS to "usual care" to 7 days.

7.2 Efficacy methods

All data will be extracted from each patient's medical record and entered into a case report form. No specific testing is defined. Data to be extracted to assess efficacy is:

- 1) Requirement for Instilled Surfactant to 72 hours of age.

- Number of patients requiring surfactant instillation from randomization to 72 hours of age. Intubation and instillation is indicated if there is a continuing, > 1hour, requirement for >40% inspired oxygen plus continuing positive pressure support to maintain acceptable blood oxygen saturations.

2) Measures of Severity of RDS from Randomization to Surfactant Instillation or 72 hours of age.

- (a) Supplemental oxygen measured as the increase and/or decrease over time.
- (b) Duration of positive pressure respiratory support over time.

3) Duration of RDS to 7 days of age :

- (a) Time from birth to when patient last required >25% oxygen.
- (b) Requiring >25% oxygen for ≥7 days (168 hours) from birth shall be defined as “unresolved RDS”.

4) Incidence of pulmonary complications to 7 days of age

- (a) Occurrence(s) of radiologically or clinically diagnosed pneumothorax, pneumomediastinum, pulmonary interstitial emphysema, subcutaneous emphysema or pneumopericardium.
- (b) Pulmonary hemorrhage defined as gross bleeding from the airway, changes in a chest X-ray consistent with pulmonary hemorrhage and acute deterioration of respiratory function.
- (c) Acute pneumonia defined as acute deterioration of respiratory function accompanied by clinical and chest X-ray findings consistent with bacterial pneumonia and a clinical decision to institute appropriate antibiotic therapy for acute pneumonia.

8. ASSESSMENT OF SAFETY

8.1 Parameters

Adverse Events During Aerosolization.

- 1) Discontinuation of aerosolization before the full dose is given for any reason
- 2) Incidence, magnitude and duration of adverse cardiopulmonary effects:
 - (A) Hypoxemia defined as O₂ saturation of < 80 % for >1 minute despite interventions.
 - (B) Airway obstruction defined as blockage of ventilation for >1 minute producing hypoxemia and bradycardia and requiring endotracheal suctioning and/or re-intubation.
 - (a) during Infasurf aerosolization(s)
 - (b) during instillation(s)
 - (C) Other.

Other safety parameters: These data will be extracted from the medical record of each patient from birth to 28 days of life, death or discharge (whichever is first).

- 1) Incidence of pneumonia, sepsis or other major infection to 28 days
- 2) Incidence and severity of seizures, brain hemorrhages or other brain injuries
- 3) Incidence and severity of necrotizing enterocolitis
- 4) incidence and severity of bronchopulmonary dysplasia.
- 5) Incidence and severity of any other severe unexpected adverse events.

8.2 Methods Identification of all safety outcomes will be by review of the patient’s medical record.

8.3 Analysis Severe, unexpected adverse events. Any severe, unexpected adverse event occurring to aerosolized assigned patients will be immediately reported to the medical director of a participating site. The medical director will review the adverse event and determine if it is related, or possibly related, to the administration of aerosolized Infasurf. If the event is considered “related” or “possibly related” the sponsor will be immediately notified and will be responsible for filing the appropriate notification to FDA. The sponsor will provide the same information to the study chair and to the other study sites. The local site P.I. will be responsible for providing the local IRB with the information about the event.

Non-serious adverse events By regulation an “adverse event means any untoward medical occurrence associated with the use of a drug in humans, whether or not considered drug related.” (21 CFR 312.32(a)).

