4.6 Stopping Rules

Individuals: Aerosolization will require the usual bedside monitoring by NICU devices and personnel appropriate for all patients in the first hours of life with significant respiratory difficulty. Any patient, who in the judgment of the clinical care team, is experiencing an adverse event due to the aerosolization will have it stopped and not restarted. Taking appropriate remedial steps to resolve an adverse event will be the responsibility of the patient’s clinical care team. The patient will not receive additional aerosol therapy if dosing is discontinued due to an adverse event.

Sites. Following an adverse event resulting in discontinuation of aerosol therapy, recruitment by that site will automatically be suspended.

The Principal Investigator (or a co-investigator) will notify the sponsor within 24 hours of the adverse event. The Sponsor will notify the Study Chair and the Chair of the Data Monitoring and Safety Committee (DMSC) within 24 hours of receiving notification.

The site will not re-start recruiting to the study until the site P.I., the Study Chair and the Sponsor decide that appropriate remediation, if necessary, has been achieved.

Any adverse event during aerosolization will be reviewed by the NICU Medical Director at the site within 24 hours of occurrence. S(he) shall contact and consult with the Study Site P.I. and after that review either allow the study to continue recruiting or suspend the study. In either case the local IRB and the Medical Director of the Sponsor will be notified within 24 hours. If the study is suspended it will not be restarted until the NICU medical director, the site P.I., the local IRB, and the Sponsor have all approved the decision to restart the trial at that site.

In addition, if the study is suspended at any one site the Sponsor will notify the P.I. at all other participating sites and the national and all local IRBs. Any local IRB, site P.I. or the Sponsor can suspend the study at any or all of the other participating sites. If suspended at other sites restarting will require prior approval by the local IRB and P.I. and the Sponsor.

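### Section 8.1 lists every incomplete aerosol dose as an adverse event whatever the cause, in conflict with 8.3, 5.3 and the procedure note

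*Combined protocol and SAP*

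**What the plan says.** Section 8.1 opens with a list headed "Adverse Events During Aerosolization". Item 1 is "Discontinuation of aerosolization before the full dose is given for any reason". Item 2 covers cardiopulmonary effects, with thresholds for hypoxemia and airway obstruction.

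Other places treat adverse events differently:

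- **8.3** quotes the regulatory definition: "adverse event means any untoward medical occurrence associated with the use of a drug in humans, whether or not considered drug related".
- **5.3** has one item for parents, "If a parent rescinds permission a patient's participation in aerosol therapy ceases", and a separate item for an adverse event that requires aerosolization to be discontinued.
- **4.6, Individuals** concerns a patient who, in the care team's judgment, "is experiencing an adverse event due to the aerosolization will have it stopped and not restarted".
- **Appendix A, procedure note** has one field for whether the aerosolization was completed and another for whether there was an adverse event. Free text is requested only if there was one.

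Five provisions then depend on the term:

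- **4.6, Sites:** "Following an adverse event resulting in discontinuation of aerosol therapy, recruitment by that site will automatically be suspended".
- **4.6, Sites, later paragraph:** the NICU Medical Director reviews any adverse event during aerosolization within 24 hours and either lets recruitment continue or suspends it.
- **4.6, Entire Trial:** the Study Chair, the safety board chair and the sponsor confer after an adverse event that results in discontinuation. Any one of them can have recruitment suspended.
- **6.1, Re-dosing, condition 3:** "no adverse event during the initial dose".
- **9.1, Primary safety analyses:** all adverse events are recorded and tabulated.

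**The concern.** Item 1 turns a delivery outcome into a safety event. A dose cut short by a device fault, a staffing problem or a parent's decision need involve no harm to the infant, yet it carries the same label as hypoxemia.

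Three things are at stake. First, the adverse-event table gains a category that only the aerosol arm can contribute to, since usual care has no dose to stop. That clouds objective (c) in section 3, that aerosol is as safe as usual care. Second, rules that act on any adverse event may act on events unrelated to safety. Third, sites that follow 8.1 and sites that follow 8.3 or the procedure note may code the same stop differently, so counts would vary with reading habits as well as with what happened.

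**Working it through.** **1. Which provisions does a non-toxic stop reach?** Take a stop not brought about by any untoward medical occurrence, such as a device fault, a staffing gap or parental rescission. Under 8.1 item 1 it is an adverse event. Each provision is then read on its plain wording.

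| Provision | Causal wording? | Reached? |
|---|---|---|
| Adverse-event tabulation (9.1) | None | Yes, aerosol arm only |
| Medical Director review, discretionary suspension (4.6) | None | Yes |
| Re-dosing condition 3 (6.1) | None | Yes, for a stop of the initial dose |
| Individual stopping rule (4.6) | Event must be due to the aerosolization | No |
| Withdrawal item 3 (5.3) | Event must require discontinuation | Not on plain wording |
| Automatic site suspension (4.6) | Event must result in discontinuation | Ambiguous |
| Trial-wide conference (4.6) | Event must result in discontinuation | Ambiguous |

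The last two are ambiguous because the stop is itself the listed event. It satisfies the rule only if it is treated as its own cause.

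The Medical Director route has knock-on effects. The local IRB and the sponsor are notified whatever the decision. If a site is suspended, all other sites and IRBs are told, and any local IRB, site investigator or the sponsor may suspend elsewhere. Each suspension on this route is discretionary.

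**2. Can the forms separate the causes?** Case report tables 3A to 3C record the dose in mL and whether aerosolization was interrupted. Tables 3B and 3C add a row for whether the full dose was given; 3A, as shown, does not. No table has a coded reason. The procedure note records completion for every dose, but asks for a description only when an adverse event is declared. A site that does not regard a technical stop as an adverse event therefore need not record why the dose ended.

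**3. How plausible are such stops?** From 6.1, the dose is 6 mL/kg at about 0.19 mL/min: 6 / 0.19 = 31.6 min/kg, which reproduces the stated figure of about 32. That is 47 minutes at 1.5 kg and 95 minutes at 3 kg, with up to two re-dosings. The pilot result in 2.3 (over 30 patients, no discontinuation for interference with breathing) does not address other causes.

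**4. How many?** Sections 9.1 and 9.2 give 229 per group in one cohort and 200 infants at 1:1 in the other: 229 + 200/2 = 329 first aerosol doses at most. The rate *p* of non-toxic stops is an assumption. Expected number = 329*p*; chance of at least one = 1 − (1 − *p*)^329, taking doses as independent.

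| Assumed *p* | Expected stops | Chance of at least one |
|---|---|---|
| 0.5% | 1.6 | 81% |
| 1% | 3.3 | 96% |
| 2% | 6.6 | 99.9% |
| 5% | 16.5 | >99.9% |

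These are chances of an early stop, not of a suspension.

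**The case against.** The strongest reply has five parts.

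- **Section 8.1 is titled as a list of parameters.** Item 1 could be only something to summarise, leaving 8.3 as the sole definition. This is a fair reading, but the other measures sit under their own separate heading, while item 1 sits under the adverse-event one. Both readings are open, and that is the problem.
- **Capturing every early stop is sensible in an unblinded trial.** It avoids bedside attribution, and 2.3 accepts that the aerosol may itself interfere with breathing. This stands, and is why every incomplete dose should still be recorded.
- **The practical harm is limited.** Re-dosing also needs a positive response to the previous dose and later deterioration, and a parent's rescission ends aerosol therapy anyway. Hypoxemia and airway obstruction are listed separately, so they remain visible. Adverse events are only tabulated, with no between-arm test planned. All of this stands and lowers the weight of the point.
- **The forms are not blank.** Volume given, completion status and conditional free text allow partial reconstruction. This stands; what is missing is a reason recorded for every incomplete dose.
- **Progression of RDS to intubation mid-dose is not a clean example.** It may well be an untoward medical occurrence under 8.3, which applies whether or not the event is considered drug related. This also stands.

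A reader might infer that any incomplete dose automatically suspends the site and convenes the trial-wide conference. The documents do not support that. Both rules require an event that results in discontinuation, and 5.3 separates parental rescission from adverse-event discontinuation. Nor does item 1 cover a pause after which the full dose is given.

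**Conclusion.** The conflict is real but minor. Item 1 of 8.1 carries no harm or causal condition and disagrees with 8.3, 5.3 and the procedure note. On plain wording a non-toxic stop enters the adverse-event table for the aerosol arm, falls under the Medical Director review, and, if it ends the initial dose, fails the re-dosing condition. Its reach to automatic site suspension and the trial-wide conference is unclear, not established.

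The expected number, about 1.6 to 16.5 across the aerosol arms, rests entirely on assumed rates of 0.5% to 5% and on full enrolment with every assigned infant starting a first dose. Sample size, alpha and the primary analysis are unaffected. The gain from correction is an interpretable safety table and consistent coding across sites.

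**What to change.** Keep capturing every incomplete dose, but report it by reason as a delivery and tolerability outcome, separate from the adverse-event counts. Suitable reasons are: untoward medical occurrence, progression of RDS to intubation, device or technical, parent or physician withdrawal, other. Any untoward medical occurrence that led to the stop stays in the adverse-event counts in its own right.

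Add a coded reason to case report tables 3A to 3C and to the procedure note, asked whenever a dose is incomplete, and add the full-dose row to 3A.

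The sponsor must reconcile 4.6 (Individuals, Sites and Entire Trial), 5.3, 6.1, 8.1, 8.3, 9.1 and Appendix A to one event definition. Which events trigger suspension or bar re-dosing is for the sponsor to settle; this review takes no position on it.

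The cost is a wording change, one new field and one added row, completed by staff who already write the note. The downside is that a safety-related stop could be coded as technical. Listing all incomplete doses with their reasons for the existing safety committee limits that risk.

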2.3 Potential Risks

It is possible that some patients will have their respiratory status worsen when aerosolized Infasurf is administered because of physical interference with ventilation. Constant, direct monitoring of the patients by health care professionals during the aerosolization is included in the protocol so that such events will be immediately recognized, the aerosolization discontinued and appropriate interventions immediately implemented to restore optimal breathing. Pilot studies of over 30 patients resulted in no patient developing interference with breathing that required discontinuation of the aerosolization.

Infasurf is unchanged in any way by aerosolization. Aerosolized Infasurf deposits only in the lung (the site of its activity) or in the stomach. There are no additional risks from Infasurf delivered as an aerosol than there are from Infasurf when instilled into the lung.

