2.7 Study Population

Patients will be recruited who:

- (a) have a clinical diagnosis of RDS,
- (b) are receiving respiratory support: supplemental oxygen plus (a) nasal continuous positive airway pressure (NCPAP), or high flow nasal cannula (HFNC) or non-invasive ventilation (NIV) to assist breathing
- (c) are not intubated and receiving mechanical ventilation for respiratory failure.

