3. OBJECTIVES AND PURPOSES OF THE TRIAL

For newborn infants born with a deficiency in lung surfactant because of prematurity or other causes of delayed lung maturation lung surfactant replacement therapy is life saving.^{2,3,4} The objective of this trial is to demonstrate that there is a group of patients who can benefit from surfactant replacement therapy with lower risk of administration complications and less discomfort by utilizing an alternative, safer administration technique – aerosolization.

Currently surfactant replacement therapy requires instillation of a liquid suspension into the airways. In order to instill into the airways it is necessary that an endotracheal tube be inserted and the surfactant administered through the endotracheal tube. A single dose may not be sufficient therapy and, if repeat dosing is likely or inevitable, a decision has to be made to either prolong the time of intubation or to remove the tube and possibly subject the patient to re-

intubation. One purpose of this trial is to determine if aerosolizing Infasurf provides an effective alternative for some patients that enable delivery of surfactant replacement therapy without subjecting them to the pain, discomfort and risk of endotracheal intubation or re-intubation.

The volume of the liquid instillation of the currently approved surfactants (2.5 to 4.0 mL/kg body weight) is larger than the total volume of the airways below the trachea which is 1 ml/kg body weight. Complications at administration are the physiologic consequences of two processes: (a) liquid obstruction of some airways, and (b) stimulation of irritant receptors in the lung. Liquid obstruction can produce transient low blood oxygen and high blood carbon dioxide, which together with neurally mediated irritant reflexes result in transient cardiopulmonary dysfunctions: cyanosis, tachycardia, bradycardia, hypotension, hypertension, airway obstruction and reflux of surfactant. Aerosolized delivery has the potential of minimizing both airway obstruction by liquid and the stimulation of irritant receptors in the lung.

Specifically the Objectives of the Trial are:

- (a) Document superiority of aerosolized of Infasurf to usual care in early RDS in preventing the need to intubate and instill a liquid surfactant suspension into the patient.
- (b) Show acute improvement in respiratory function by aerosolized Infasurf.
- (c) Document that aerosolized Infasurf is as safe as “usual care” for RDS patients.

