15 APPENDICES

APPENDIX A

Intervention Notes Formats

Initial Aerosol Procedure Note

Date Time: Patient was randomized to the Aerosolization Group in the Aerosolized Infasurf Trial in the {never treated} {previously instilled} cohort. The initial aerosolization was started at ___:___ hours and was completed at ___:___ hours. A total of ___ mL of Infasurf was aerosolized. The Inspired O₂ prior to starting the aerosol was ___%. The aerosolization {was} {was not} completed. There {was no} {was an} adverse event during the aerosol delivery. {If present describe in detail}.

Repeat Aerosol Procedure Note

Date Time: A repeat aerosolization was started at ___:___ hours and was completed at ___:___ hours. A total of ___ mL of Infasurf was aerosolized. The Inspired O₂ prior to starting the aerosol was ___%. The aerosolization {was} {was not} completed. There {was no} {was an} adverse event during the aerosol delivery. {If present describe in detail}.

Usual Care Procedure Note

Date Time: Patient was randomized to the Usual Care Group in the Aerosolized Infasurf Trial in the {never treated} {previously instilled} cohort. The Inspired O₂ at the time of randomization was ___%.

Aerosolized Infasurf Trial Case Report

1. Identity Data

Last Name _____

Date of Birth ____/____/____

Time of Birth ____:____

Hospital # _____

Study # _____

Consent # _____

Strata A B

Rx Group Usual Care Aerosolized

2. Demographic Data

Sex M F

 Single MultA MultB MultC

Birth Wt _____grams

Gestational Age ____wks ____days

Maternal Steroids N <12 hrs >12 hrs

Delivery: Vaginal C-Section

APGAR ____ 1min ____ 5 min

Intubated in DR Y N

Surfactant in DR Y N

3 A. 1st Aerosolization Procedure Data

Date		
Start time		
End time		
Patient Age (hrs)		
Dose (mL)		
Aerosol duration (min)		
Mode of Support		
FiO2	Pre	
	30 min	
	60 min	
	90 min	
	120 min	
	180 min	
	240 min	
Aersolization interrupted		

3 B. 2nd Aerosolization Procedure Data

Date		
Start time		
End time		
Patient Age (hrs)		
Dose (mL)		
Aerosol duration (min)		
Mode of Support		
FiO2	Pre 1	
	30 min	
	60 min	
	90 min	
	120 mins	
	180 min	
	240 min	
Aersolization interrupted		
Full dose given		

3 C. 3rd Aerosolization Procedure Data

Date		
Start time		
End time		
Patient Age (hrs)		
Dose (mL)		
Aerosol duration (min)		
Mode of Support		
FiO2	Pre 1	
	30 min	
	60 min	
	90 min	
	120 mins	
	180 min	
	240 min	
Aersolization interrupted		
Full dose given		

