4. Respiratory Status Randomization From Birth to 72 Hours of Age for All Patients
(source respiratory and nursing sheets or charts)

Date	Time	Age (hrs)	FIO ₂	CPAP	HFNC >2/kg/min	Non-invasive ventilation	Mechanical ventilation/oscillation
		6					
		12					
		18					
		24					
		36					
		42					
		48					
		54					
		60					
		66					
		72					

5. Endotracheal Intubations +/- Surfactant Instillation (source procedure note)

# previous intubations	Age (hrs)	FiO ₂	Surfactant (Inf,Curo,Surv)	Surfactant Dose (ml/kg)	Complications of Surfactant Instillation* (all that apply)
0					
1					
2					

* 1=cyanosis; 2=bradycardia, 3=reflux, 4=airway obstruction 5= hypotension 6= re-intubated 7=required CPR

6. Imaging Results Days 1-4 (source report of radiologist interpreting the image(s))

Imaging	Day 1		Day 2		Day 3		Day 4	
	Normal	Abnormal	Normal	Abnormal	Normal	Abnormal	Normal	Abnormal
Chest X-ray(s)								
Head ultrasound(s)								
Other ultrasound(s)								
Other X-ray(s)								
CT scan(s)								
MRI (s)								

[figure not shown]
[figure not shown]
Chest X-Ray abnormality is defined as a diagnosis, not just a description (1)RDS; (2)pneumothorax (3)PIE (4) pneumomediastinum (5) pneumonia (5) interstitial edema (6) pulmonary hemorrhage (7) other

Head ultrasound abnormality (1)IVH grade 1 or 2 (2) IVH grade 3 or 4 (3) PVL (4) HIE (5) cerebral edema (6) other

7. Patient Outcomes on Days 4, 8, and 29 of Life and Discharge Summary
 (source progress notes on days 5, 9, and 29 or discharge (D/C))

Organ System	Diagnoses	Day 4	Day 8	Day 29 or D/C
Status	(1)Alive (2)Deceased (3)Ventilated (4)On CPAP/HFNC/NIV (5)On O ₂ for RDS (6)On O ₂ for apnea (7)Other			
CNS	(1)IVH-1/2 (2)IVH-3/4 (3)HIE (4)PVL (5)Seizures (6)Apnea (7)Cerebral edema (8)Other			
Respiratory	(1)RDS (2)Pneumothorax (3)PIE (4)Pneumonia (5)Pulmonary hemorrhage (6)Pneumomediastinum (7)BPD (7) Other			
Cardiovascular	(1)CHF (2)Hypotension (3)Hypertension (4)PDA (5)PDA Rx drugs (6)PDA Rx surgery (7)Arrhythmia (8)Other			
GI	(1)NEC stage 1 (2)NEC stage 2 (3)NEC stage 3 (4)GI bleeding (5)diarrhea (6) GE reflux (7)other			
Renal	(1)Oliguria/anuria (2)Uremia (3)Hypernatremia (4)Hyponatremia (5)Hyperkalemia (6)Hypokalemia (7)Other			
Metabolic	(1)Hypoglycemia (2)Full parenteral feedings (3)Partial parenteral feedings (4)Full oral feedings (5)Other			
Hematologic	(1)Neutropenia (2)Thrombocytopenia (3)Coagulopathy (4)Other			
Infection	(1)Sepsis (2)Meningitis (3)Cellulitis (4)Other			

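### Airway obstruction in 8.1 item 2(B) depends on endotracheal suctioning or re-intubation, and only instillations have coded complications, so obstruction counts for aerosol and instillation are not comparable

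*Combined protocol and SAP*

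**What the plan says.** Section 8.1 lists adverse effects to be recorded around administration. Item 2(B) is airway obstruction, defined as "blockage of ventilation for >1 minute producing hypoxemia and bradycardia and requiring endotracheal suctioning and/or re-intubation". As laid out, it has two sub-lines, one for aerosolizations and one for instillations, under the same definition.

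Section 2.7 recruits infants who "are not intubated and receiving mechanical ventilation for respiratory failure", and section 5.1 requires both cohorts to be free of a tube at entry.

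The case report form treats the two procedures differently:

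- Section 5 (intubations and instillations) has a tick-all-that-apply complications column with seven codes: "1=cyanosis; 2=bradycardia, 3=reflux, 4=airway obstruction 5= hypotension 6= re-intubated 7=required CPR". The form puts no threshold on code 4.
- Sections 3A to 3C (first to third aerosolization) record times, dose, support mode, serial FiO2 and "Aersolization interrupted"; 3B and 3C also show a full-dose field. None has a complication code.
- The Appendix A aerosol procedure note has a yes/no adverse-event entry, with free text if the answer is yes.

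Section 2.3 says that some infants' respiratory status may "worsen when aerosolized Infasurf is administered because of physical interference with ventilation". Section 3 states the trial's aim as surfactant therapy with "lower risk of administration complications and less discomfort". Section 9.1 plans to tabulate adverse events, with no test or margin.

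**The concern.** An event definition used for two procedures should be equally reachable in both. This one ends in a condition about an airway device that is present in one procedure and absent in the other. The missing episodes would all come from aerosolizations, and they concern the one aerosol risk that section 2.3 names.

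The form adds a second asymmetry. An obstruction during instillation has a box to tick. One during aerosolization has to be found in narrative text.

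Because the safety analysis is tabulation only, definitions and coding decide what the tables show. A lower obstruction count for aerosol could not be told apart from an effect of the counting rule, and the aim in section 3 invites a reader to interpret it as a real difference. Treatment is unmasked (4.3), which makes symmetric, objective criteria more important.

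**Working it through.** The documents give no expected rate, sample size or power for administration events, so there is no stated figure to reproduce. The check compares the texts and then gives an illustration on assumed rates.

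**1. One episode against the definition.** Take a blockage lasting over a minute with hypoxemia and bradycardia.

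| Situation | Tube in place? | How relieved | Counted under 2(B)? |
|---|---|---|---|
| Instillation | Yes | Tube suctioned | Yes |
| Aerosolization | No | Without a tube | No |
| Aerosolization, intubated before (Cohort 2) | No | Tube placed | Yes, as a re-intubation |
| Aerosolization, never intubated before | No | Tube placed | Unclear: literally a first intubation |

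The first two rows carry the point. The last is a matter of wording and is not relied on below.

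**2. Coded capture per procedure.** Instillation has 7 codes and aerosolization has 0. This shows that the instruments differ; it does not measure bias. The documents also do not say whether the 8.1 definition governs code 4. If it does not, an instillation obstruction can be ticked with no duration or severity test.

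**3. Illustration of the loss under 2(B).**

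- Planned aerosol infants, from sections 9.1 and 9.2 with 1:1 allocation: 458/2 + 200/2 = 229 + 100 = 329.
- Assumed: true obstruction rate r, at one event per infant, and share f relieved without endotracheal suctioning or intubation. The documents give neither.
- Counted events = 329 × r × (1 − f).

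| r | True events | f = 0 | f = 0.5 | f = 1 |
|---|---|---|---|---|
| 2% | 329 × 0.02 = 6.58 | 6.58 | 3.29 | 0 |
| 5% | 329 × 0.05 = 16.45 | 16.45 | 8.2 | 0 |
| 10% | 329 × 0.10 = 32.9 | 32.9 | 16.45 | 0 |

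Section 2.3 reports that none of more than 30 pilot infants had interference requiring discontinuation. With n = 30, the one-sided 95% upper bound is 1 − 0.05^(1/30) = 9.5%. That event differs from 2(B), so the bound only shows that the pilot does not rule out rates of this order.

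**4. Allowing for the other safety lines.** Let g be the assumed share of episodes missed by 2(B) that appear elsewhere in the safety data. The share lost from all lines is f × (1 − g). With f = 0.5:

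- g = 0 gives 0.5 × 1 = 50%
- g = 0.9 gives 0.5 × 0.1 = 5%
- g = 1 gives 0%

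The loss under the obstruction label stays at 50% in all three cases.

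**The case against.** The strongest reply is that these episodes are recorded elsewhere.

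- Section 8.1 item 1 counts any aerosolization stopped short of its full dose, whatever the cause. Section 4.6 has the aerosol stopped when the care team judges that it is causing an adverse event.
- Item 2(A) counts saturation below 80% for over a minute despite intervention, with no tube condition. If hypoxemia in 2(B) carries that meaning, every episode of the kind described also meets 2(A).
- Item 2(C) takes other events, each aerosol procedure note has the yes/no entry, daily progress notes are uploaded, and section 9.1 tabulates all adverse events.
- Section 4.6 requires review within 24 hours of any event during aerosolization and states no counterpart for instillation. That could raise ascertainment on the aerosol side.
- Objective (c) compares aerosol with usual care, and no test of aerosolization against instillation is planned.

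All of this stands, and it limits the conclusion. A reader might infer that administration harm from aerosol as a whole is under-counted, or that an obstruction relieved without a tube has no chance of being recorded. The documents support neither reading: the episode fails the 2(B) label and can still enter the safety data by several routes.

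These routes do not make the obstruction counts comparable. Discontinuation mixes airway and other causes and has no instillation counterpart. If hypoxemia in 2(B) has its ordinary meaning, a brief dip below 80% misses 2(A). Item 2(C) and the notes are uncoded. Section 4.6 is a notification and suspension process and does not alter 2(B). The absence of a formal test does not help either, since a tabulated count is still read as a comparison.

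**Conclusion.** The point holds for the obstruction item and for the recording forms. Applied as written, 2(B) leaves out aerosol obstructions relieved without a tube and counts the same episode during instillation once the tube is suctioned. The obstruction count is therefore likely too low for aerosol, and coded complications cannot be compared between the two procedures.

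The loss under 2(B) equals f, the share of aerosol obstructions relieved without endotracheal suctioning or intubation, and could be anything from none to all. The documents do not give f or the true rate. Across all safety lines, neither the size nor the net direction of bias can be determined, because other routes catch some episodes and aerosol events receive extra scrutiny.

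This should be fixed. It affects a descriptive safety item tied to a named risk and a stated aim. The primary endpoint, its test and the sample size are unaffected.

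**What to change.** - In 8.1 item 2(B), define airway obstruction by the event: blockage over 1 minute with hypoxemia and bradycardia. Remove the endotracheal suctioning or re-intubation condition from the definition.
- Record the intervention used as a separate field, distinguishing a first intubation from a re-intubation.
- Use one coded complication list for every aerosolization (case report sections 3A to 3C and the Appendix A aerosol notes) and every instillation (section 5).
- State whether the 8.1 definition governs code 4 in section 5.

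These changes affect measurement only. They add no test or visit, in keeping with section 4.9. The cost is one reworded definition and a few more form fields, and the recorded aerosol obstruction count may rise.
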